researchers and with input from the PPI contributors, each transcript will be coded by one researcher and a sample of these transcripts will be reviewed independently by a second researcher. The thematic analysis²⁶ will be conducted by the small team of three members of research staff who conducted the interviews. These researchers will initially identify themes, which will then be discussed with other members of the research team and the PPI groups. The audio/video-recorded consultations will also be fully transcribed and analysed thematically, as described above. An observation guide will support analysis of the fidelity of use of the template. In addition to assessing fidelity, we will analyse the recordings of consultations to look for evidence of having received training, considering the variation in training and how this may have affected the practices' experience of, and approach to, using the template and patients' experience of the reviews. We will also look for evidence of use of person-centred consultation skills.

The routine data will be used to understand the adoption, reach and fidelity of implementation. This will include exploring the proportion of eligible patients who were invited to a review, the proportion that attended, and the extent to which key elements of the template were completed. We will also explore whether there are particular patient groups who were more or less likely to receive a complete review as intended. As far as possible, the quantitative analysis will include the items specified within the Finance, Commissioning and Contracting Handbook for Personalised Care (e.g. % eligible people receiving a personalised care plan, % referred to social prescribing link-workers).²⁷

In the pre-intervention period, most patients will have been invited to an annual review consultation based on a pre-existing template, but this would rarely lead to provision of a care and support plan. The intervention consists of patients being invited for an annual review using the new template, which encourages provision of a care and support plan. Over the study time period, the number of eligible patients being invited for an annual review consultation based on the new template (the intervention) should increase. Some of these patients will receive a care and support plan (the primary outcome).

Comparative analyses using the routinely recorded data will explore whether the primary outcome of receipt of a personalised care and support plan differs between patients in intervention and control practices. Negative binomial regression will be used to assess the number of patients receiving a plan in each practice in each time period (2021/22 vs. 2022/23), in a difference-in-difference analysis framework. Intervention (a binary variable indicating intervention or control practices), period (2021/22 vs. 2022/23), and the interaction between the two will be fitted as fixed effects, with practice as a random effect. As the same patients will appear in both time points, no adjustment for age, sex, etc is required. Whether the effect of year differs within particular patient groups will be explored by fitting the patient group variable (e.g. sex) as well as additional interactions, in the model, all as fixed effects.

A second set of comparative analyses will look at the impact on practice workload, including frequency, duration, and type of consultation, as well as the staff group who performed the consultation. Further, the number of regular reviews for specific diseases, and the number of fidelity type measures (e.g. mood and memory) and drugs prescribed will be explored, among other indicators. We will explore whether use of the template has any impact on clinical indicators of high quality care, such as blood pressure control or diabetic control. Subgroup analyses (e.g. exploring telephone consultations only) will be analysed as separate models for each subgroup of interest.

For all methods outlined, underlying assumptions in statistical models will be checked using standard methods, e.g. residual plots, etc. If assumptions are not valid, alternative methods of analysis will be sought.

The patient questionnaire will be used to quantify patient-reported outcomes before and after receiving the patient-centred multimorbidity review. Simple descriptive statistics will illustrate the health difficulties that patients with multimorbidity report most commonly. We will also explore whether there is a change in patient experience after the review, using similar models as described above.

We will estimate implementation and delivery costs of the annual review intervention, and explore the wider impact on healthcare resources, from an NHS perspective. We will explore the possibility of including social care data as well, depending on the availability of linked data. The implementation

cost per GP practice will include administration and practice staff training to deliver the annual review intervention. The delivery cost per patient will include staff time, medication costs and investigations associated with delivering the annual review, and any further healthcare contacts instigated during the review.

Impact on wider healthcare resource use: in addition to the implementation and delivery costs, the intervention may lead to changes in healthcare use (e.g. (i) at an aggregate level, (ii) between primary and secondary care, or (iii) between elective and emergency care). We will use regression models to compare measures of healthcare cost during the postintervention period for patients who received the intervention and those who did not, in intervention and control practices. The post intervention period will be defined as the month of the patients' birthdate to the end of the data collection period. Models will account for baseline healthcare costs (those in the same period in the previous year) and patient and practice characteristics.

As described above, anonymised primary care data, including consultation duration, will be collected from practices' EMIS software (either directly by each practice, or via a system wide dataset), and we will seek to collect secondary care data from a system wide data set where available or the NHS Secondary Uses Service (SUS). Administration costs and time for practice staff training will be estimated from data collected by the research team. Staff time and medication costs will be based on national estimates,^{29,30} and investigations will be costed using national estimates²⁹ or literature. Secondary care data will be costed using national tariffs.³¹

10) ETHICAL AND REGULATORY CONSIDERATIONS

This is an implementation project which seeks to explore how best to implement a computerised template, and to study the impact of implementing the template. The template itself is already in use and this project aims to improve the template and to study how to improve its implementation, with a view to supporting the ultimate aim which is to improve the personalisation of care. In most respects this can be considered a service improvement project, but we are seeking NHS ethics approval because the study is designed to produce generalisable or transferable findings beyond those practices included in the study.

The intervention itself does not raise any risks for patients beyond usual care. The decision to use the template, and clinical decisions which are connected with use of the template, are entirely at the discretion of the clinician consulting with the patient.

The routinely collected data will be pseudonymised (linked anonymous) and identifiable only by the patient's clinical team, not by the research team. We will ensure that we do not collect data that could in combination have a significant risk of making the patient identifiable.

The patient and staff interviews or questionnaire survey do not raise any ethical issues beyond the usual requirement to obtain fully informed consent.

The collection of recordings of general practice consultations raises ethical issues. We have considerable experience of collecting this type of data, for example in the 'one in a million' project http://www.bristol.ac.uk/primaryhealthcare/researchthemes/one-in-a-million/. We will ensure that patients are fully aware of how their data will be stored and used and give fully informed consent as described under 'Consent' on page 22.

Assessment and management of risk

Potential risks from the study are described below. We will maintain a register which records details of any events of this type, how we responded and who we passed the information on to.

Risk Miti	igation
-----------	---------

We identify patients who appear to have serious medical problems which have not been addressed.	We will draw this to the attention of the GP within the practice responsible for the patient's care
While undertaking an interview, or in a questionnaire response, we identify a patient or member of staff who appears to be at risk of suicide or of harming other people	If the risk relates to a patient, we will draw this to the attention of the GP within the practice responsible for the patient's care. If the risk relates to a member of staff we will draw this to the attention of the senior partner (or other partner if the senior partner is the person at risk).
While undertaking an interview, or in a questionnaire response, we identify a safeguarding concern eg in relation to child or adult abuse, domestic violence or other potential patient harms which the practice is not already responding to.	We will draw this to the attention of the GP within the practice responsible for the patient's care
We are given information which makes a patient identifiable, without their consent	We will immediately delete any information which makes the patient identifiable, and inform the practice's data protection officer for them to address this breach in line with their data protection policy.

Health Research Authority (HRA), Research Ethics Committee (REC) and other Regulatory approvals & reports

Before the start of the study, a favourable opinion will be sought from an NHS Research Ethics Committee and the HRA

All correspondence with the REC/HRA will be retained.

An annual progress report (APR) will be submitted to the REC/HRA within 30 days of the anniversary date on which the favourable opinion was given, and annually until the study is declared ended.

The Chief Investigator will notify the REC/HRA of the end of the study.

If the study is ended prematurely, the Chief Investigator will notify the REC/HRA, including the reasons for the premature termination.

Within one year after the end of the study, the Chief Investigator will submit a final report with the results, including any publications/abstracts, to the REC/HRA.

Regulatory Review & Compliance

Before any site can enrol patients into the study, the Chief Investigator/Principal Investigator or designee will ensure that appropriate approvals from participating organisations are in place.

Amendments

The sponsor (University of Bristol) is responsible for deciding whether an amendment is substantial or non-substantial for the purposes of submission to the REC.

For any amendment to the study, the Chief Investigator or designee, in agreement with the sponsor will submit information to the REC/HRA in order for them to issue approval for the amendment.

In case of the need for a substantial amendment to the protocol, we will submit a valid notice of amendment to the REC for consideration. Substantial amendments that require review by NHS REC/HRA will not be implemented until that review is in place and other mechanisms are in place to implement at sites.

Non-substantial amendments that require review by the Sponsor will not be implemented until that review is in place and other mechanisms are in place to implement at sites.

We will notify each participating general practice of approved substantial amendments, and nonsubstantial amendments where they affect research procedures within the practice. The Chief Investigator or designee will work with practices to implement the amendment and to confirm their support for the study as amended, as appropriate

Changes to the protocol as a result of amendments (both substantial and non-substantial) will be recorded at the beginning of this protocol.

Peer review

This study was funded as part of a competitive process under the NIHR ARC National Multiple Long-Term Conditions Implementation Programme. As part of this process the funding panel obtained 9 independent peer reviews, including from experts and from patient representatives. The additional funding from the NIHR School for Primary Care Research was also awarded via a competitive process and peer review.

Protocol compliance

This study involves exploring how to achieve wider implementation of a service improvement which is already in use in the NHS. The multimorbidity template encourages good practice in line with current NHS guidelines and the Quality and Outcomes Framework, therefore any risks to patients are very unlikely.

Given that the eligible cohort all have multiple long term conditions, and many of them will be elderly and frail, we expect a high rate of events such as hospitalisations and deaths which are not related to the implementation of the template. We will investigate any serious adverse events (SAEs) which anyone involved with the study reports could be related to the intervention or the research procedures, whether reported by patients, practice staff or researchers. Details will be collected using an adverse events form, and a register will be kept of all events investigated and how they were resolved. The Chief Investigator is responsible for defining each event in relation to its seriousness, relatedness and expectedness.

A Serious Adverse Events (SAEs) is defined as an event that:

- results in death;
- is life-threatening;
- requires hospitalisation or prolongation of existing hospitalisation;
- · results in persistent or significant disability or incapacity; or
- consists of a congenital abnormality or birth defect; or
- is otherwise considered medically significant by the investigator.

SAE reporting is handled via a Service Level Agreement with University Hospitals Bristol and Weston NHS Foundation Trust. SAEs that are related to the study (ie they resulted from administration of any of the research procedures) and unexpected (ie not listed in the protocol as an expected occurrence) will be reported to the sponsor within 3 working days and emailed to the REC using the Non-CTIMP safety report to REC form within 15 days of the chief investigator becoming aware of the event.

Any urgent safety matters will be reported to the sponsor and REC immediately by telephone and email and confirmed in writing within 3 working days.

Data protection and patient confidentiality

All investigators and study site staff will be required to comply with the requirements of the Data Protection Act 1998 and GDPR with regards to the collection, storage, processing and disclosure of personal information and will uphold the Act's core principles.

All research data collected in each region (ARC West, ARC West Midlands, ARC Wessex, relating to the universities in Bristol, Keele and Southampton respectively) will initially be stored in encrypted files in secure password protected servers at each of the three universities. It will then be copied for collation and storage onto a PP4M project folder on the University of Bristol server. The research teams in Keele and Southampton will copy data into this folder using a virtual private network under honorary contracts with the University of Bristol which cover issues of confidentiality and data protection. Only authorised members of the research team will have password protected access to this folder. The server at the University of Bristol is stored in a locked and alarmed building.

All routinely collected data will be pseudonymised, using an identifier which can only be linked to the patient by the practice and not by the research team.

Qualitative data will include identifiable information and will only be collected and stored with patient consent. Transcripts created from recorded interviews will be pseudonymised by removing any personally identifying information such as the names of patients or staff mentioned within interviews. The transcripts will be identified using coded study identifier (study IDs). The link between the study ID and the patient or staff details will be stored separately from the research data.

Baseline questionnaire data will be entered into a database using the Redcap system and will be identifiable only by the practice code and Emis number, which can only be linked to an individual patient by members of the local clinical team.

Identifiable personal data (names and addresses) used to send follow-up questionnaires will be kept separate from the dataset of questionnaire responses and will be destroyed at the end of the project. The pseudonymised data will be stored for 10 years at the University of Bristol.

[name] will be the data custodian.

Indemnity

Insurance will be provided by University of Bristol as project sponsor. This will meet the potential legal liability of the sponsor for harm to participants arising from the design of the research. The GP surgeries will also have their own professional indemnity for their activities connected with this research project.

Access to the final study dataset

The study investigators listed as members of the core or wider research teams, (see Appendix 4) and research staff specifically employed to work on this project in Bristol, Keele or Southampton will be the only people with access to the full study dataset.

11) DISSEMINATION POLICY

The data from this study will be owned by the University of Bristol.

On completion of the study, the data will be analysed and tabulated and a Final Study Report prepared. If appropriate this may be in the form of one or more research papers submitted for peer-reviewed publication, rather than a separate report.

The Final Study Report (and/or research papers) will be made openly and freely available via the University of Bristol Research Portal, and also on a project website.

All publications must include an acknowledgement of funding and disclaimers, as agreed with the funding body and ARC West, the lead organisation.

Participants in the study will be able to see the results of the study by following the study website. Information about this website will be included within participation information at the time of recruitment.

Authorship eligibility guidelines and any intended use of professional writers

The core research team (see Appendix 4) will be responsible for drafting the final study report. The wider research team will also be listed as authors if they have contributed to the project for at least 12 months and fulfil International Committee of Medical Journal Editors (ICMJE) authorship criteria.

All participating investigators listed as members of the 'core' or 'wider' research team will be encouraged to contribute to at least one published research paper from this project, subject to conditions in the section below.

Researchers employed specifically to work on this study will also be entitled to contribute as authors to research papers.

Those listed as collaborators (see Appendix 4) will not be *entitled* to act as authors but may be *invited* to join as authors where appropriate.

All proposals for research papers must be submitted to the core research team for approval, in order to co-ordinate submissions and avoid duplication in publications.

Investigators will only have a right to publish research papers from this project if they contribute to the project for at least 12 months and if they fulfil ICMJE authorship criteria.

There is no intention to use professional writers.

12) REFERENCES

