As well as informing strategies for implementation, the NPT framework will also be used to structure the evaluation. We will combine use of NPT as a substantive theory with a realist approach which seeks to understand causal processes through elucidating context-mechanism-outcome configurations (commonly described as 'what works, for whom, and in what circumstances?').¹³ There is increasing interest in combining these approaches, although there has been limited discussion of the theoretical implications of combining these two different methods.¹³ We will add to the literature by reflecting on our experience of these methods in combination in this evaluation.

NPT is based on an implementation science paradigm, but this project also includes some strategies drawn from quality improvement methodology.¹⁴ For example, implementation and evaluation will be iterative, with repeated cycles of collecting data, feeding back findings to practice teams and making changes to the intervention in order to improve implementation.

3) RESEARCH QUESTION/AIM(S)

Aims

The research aims are:

- 1. To explore the most effective strategies to implement a template to promote personalised care in patients with multimorbidity.
- 2. To examine under what circumstances, for which patients and in what ways the template leads to benefits for patients and/or practice staff.

Objectives

- 1. To optimise an existing multimorbidity template already provided by Ardens and include more patient-centred elements in line with the NHS Comprehensive model of Personalised Care
- 2. To implement this template in general practices in three areas of England, supported by West of England AHSN, Keele Impact Accelerator Unit and local CCGs.
- 3. Through interviews with general practice staff to understand factors that lead to, or impede, implementation of the multimorbidity template in general practices in these three areas. This includes how training influences implementation.
- 4. Using the NOMAD questionnaire based on an NPT framework, to understand the extent to which the template becomes normalised within general practices
- 5. Through analysis of quantitative data from practice records, to explore the extent of implementation and factors influencing uptake of the multimorbidity template.
- 6. Through consultation observations and interviews to examine the different ways in which staff use the template

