- 7. Through qualitative research based on interviews, analysis of patient reported outcome measures and direct observation of consultations, to examine under what circumstances, for which patients and in what ways the template leads to benefits for patients and/or practice staff.
- 8. Through interviews with patients and staff, to explore how the template and its implementation could be improved to ensure wider adoption and reach.
- 9. To explore the feasibility of the Maxwell approach to broader system change to support patients with multimorbidity in a sub-set of practices which receive training from Year of Care Partnerships in addition to the template.

Deliverables

The deliverable benefits from this study will be:

- Evidence about the feasibility and potential impact of a personalised template to support review and self-management in patients with multimorbidity.
- Understanding of factors which determine the implementation of the template and the way it is used, with recommendations on how to ensure effective implementation.

4) STUDY DESIGN

This is a concurrent mixed methods study,¹⁵ in which qualitative and quantitative data collection is inter-woven in order to meet the overall study aims.

5) SETTING

General practices and their local commissioning organisations in three areas of England: Bristol/Gloucester/Somerset within ARC West; Stoke-on-Trent/Staffordshire (ARC West Midlands); Hampshire (Wessex ARC).

Bristol, North Somerset and South Gloucestershire CCG covers a diverse population of 1 million people living in a range of urban and rural areas. The CCG commissions care from 81 GP practices as well as hospital and community services. BNSSG CCG and its partners in the BNSSG Integrated Care System (ICS), are committed to supporting personalised care.

Staffordshire and Stoke-on-Trent STP includes practices in the following 6 CCGs: North Staffordshire; Stoke on Trent; South East Staffs & Seisdon; East Staffordshire; Cannock Chase and, Stafford & Surrounds. These CCGs are part of the 2 Integrated Care Partnerships (ICPs) in Staffordshire, both of whom have identified long term conditions/multi-morbidity as a priority in the restoration and transformation plans moving forward.

Hampshire and Isle of Wight Sustainability and Transformation Partnership STP) comprises NHS and local authority organisations, serving a population of >1 million people. A key priority in the STP is the development and implementation of personalised care strategies

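### The exploratory patient-group analysis names the effect of year as its target, but in the controlled difference-in-difference model the intervention effect is intervention × period

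*Protocol*

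**What the plan says.** Protocol section 9 (Data analysis) compares 2021/22 with 2022/23 by negative binomial regression of the number of patients with a plan in each practice and period, "in a difference-in-difference analysis framework". The question is whether "receipt of a personalised care and support plan differs between patients in intervention and control practices". The terms are intervention, period, "and the interaction between the two will be fitted as fixed effects, with practice as a random effect".

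The patient-group analysis follows directly: "Whether the effect of year differs within particular patient groups will be explored by fitting the patient group variable", sex being the example, "as well as additional interactions, in the model, all as fixed effects". The text does not list those interactions or say which coefficient is to be read.

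Section 3 gives the second research aim: "To examine under what circumstances, for which patients and in what ways the template leads to benefits for patients and/or practice staff". Section 9 adds that the qualitative and quantitative data together will be used to explore for whom the intervention worked.

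**The concern.** The sentence on patient groups sets its own question, and that question does not match the model it extends. The primary effect is the extra change in intervention practices over the change in control practices. A difference between groups in the effect of year is another quantity, because part or all of it is the change that would have occurred without the template.

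An analyst who follows the sentence literally would read a group × year contrast. A group whose recorded plans are rising everywhere could then be reported as benefiting more, and a real difference in benefit could be hidden by opposing trends. This would weaken what the routine data contribute to the part of aim 2 that asks for which patients the template helps.

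The wording would suit an uncontrolled before-after comparison, where the year effect is the intervention effect. The protocol's version table records that control practices were added in version 3.0 in place of such a comparison. That the sentence was carried over is only an inference, and the point does not depend on it.

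**Working it through.** **The plan's own figures.** None attaches to this analysis. The routine-data total reproduces (24 practices × 300 patients = 7200) and is not affected. The protocol gives no plan rates, so all counts below are assumptions.

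**Model.** Let A = 1 for intervention practices, P = 1 for 2022/23 and G = 1 for one of two patient groups. On the log scale, leaving out the practice effect:

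log E(Y) = α + β₁A + β₂P + β₃AP + γ₁G + γ₂GA + γ₃GP + γ₄GAP

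- Year effect in group G, control practices: exp(β₂ + γ₃G).
- Year effect in group G, intervention practices: exp(β₂ + β₃ + γ₃G + γ₄G).
- Intervention effect in group G (the ratio of these two): exp(β₃ + γ₄G).

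The intervention effect therefore differs between groups by the factor exp(γ₄), the three-way term. A group difference in the effect of year can be read in two ways, and neither gives exp(γ₄):

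1. Fit group × period without the three-way term. The result averages over arms and mixes trend with intervention effect.
2. Fit everything but read γ₃. With control practices as reference, this is the difference in control-arm trend alone.

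**Illustration.** Expected counts without noise, groups of equal size, and the same log link as the negative binomial model. Each cell starts at 10 (A to C) or 5 (D). Trend is the change ratio in control practices. Effect is the change ratio in intervention practices divided by the trend.

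| Case | Control counts, G=0; G=1 | Intervention counts, G=0; G=1 | Trend, G=0; G=1 | Effect, G=0; G=1 |
|---|---|---|---|---|
| A | 10→10; 10→15 | 10→20; 10→30 | 1.0; 1.5 | 2.0; 2.0 |
| B | 10→20; 10→12.5 | 10→30; 10→37.5 | 2.0; 1.25 | 1.5; 3.0 |
| C | 10→10; 10→10 | 10→15; 10→30 | 1.0; 1.0 | 1.5; 3.0 |
| D (G=0 men, G=1 women) | 5→20; 5→10 | 5→20; 5→40 | 4.0; 2.0 | 1.0; 4.0 |

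Contrasts between groups (G=1 relative to G=0):

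| Case | Group × period, arms pooled | Group × period, control arm | Three-way |
|---|---|---|---|
| A | (45/20)/(30/20) = 1.50 | 1.5/1.0 = 1.50 | 2.0/2.0 = 1.00 |
| B | (50/20)/(50/20) = 1.00 | 1.25/2.0 = 0.625 | 3.0/1.5 = 2.00 |
| C | (40/20)/(25/20) = 1.60 | 1.0/1.0 = 1.00 | 3.0/1.5 = 2.00 |
| D | (50/10)/(40/10) = 1.25 | 2.0/4.0 = 0.50 | 4.0/1.0 = 4.00 |

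Case A shows a group difference where the intervention effect has none. Case B hides a twofold difference under the pooled reading and points the wrong way under the control-arm reading. In case C there is no background trend, yet the pooled reading understates the difference and the control-arm reading misses it. Case D shrinks a fourfold difference to 1.25, or reverses it.

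**The case against.** The strongest reply is that the sentence does not stop at the group variable. It continues "as well as additional interactions, in the model, all as fixed effects", and the model meant already contains intervention × period. The added interactions may include the three-way term, and a list of terms is commonly left to the SAP. This stands as far as it goes. A reader might infer that the year effect is to be tested in place of the intervention effect, and the text does not establish that. It leaves the terms open. What the reply does not repair is the stated question. That question is still the effect of year, and an SAP that followed it faithfully would read the wrong contrast even from a full model.

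The analysis is also exploratory, no subgroup power is claimed, and nothing in the protocol suggests control trends that diverge as sharply as in case D. That limits the weight of the point. Case C, however, needs no divergence at all.

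Three further inferences are tempting and should not be drawn:

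- **Objective 7 rests on this model.** It is pursued "Through qualitative research based on interviews, analysis of patient reported outcome measures and direct observation of consultations". The routine-data model contributes to aim 2 but is not its only basis.
- **A patient variable such as sex cannot be fitted to practice counts.** The routine data are extracted at patient level with age group, sex, ethnicity and deprivation, so counts by group are readily obtained, and fitting sex implies them.
- **Separate models in the second set of analyses are an error.** Those subgroups "will be analysed as separate models for each subgroup of interest", but the only example is telephone consultations, where splitting the outcome is reasonable. The protocol does not say that patient or practice subgroups there will be handled this way.

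**Conclusion.** The concern holds as a misnamed target in an exploratory analysis, and it should be corrected. The protocol asks whether the effect of year differs between patient groups and does not say which interaction answers the question. In its own controlled model, the relevant quantity is the group difference in intervention × period.

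Read literally, the contrast can err in either direction: 1.50 against a true 1.00, 1.00 against 2.00, or 1.60 against 2.00 without any trend. These sizes rest on assumed counts and equal groups, so they show that the two quantities differ but do not predict by how much in this study. The algebra needs only the log link and the stated model terms. The primary effect, the sample size and the protocol's other figures are untouched. The documents do not support the stronger conclusion that the plan rules out the correct interaction or leaves aim 2 without an answer.

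**What to change.** In section 9 (Data analysis), replace the effect of year with the intervention effect and name the term to be read. For example:

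*Differences between patient groups in the intervention effect (intervention × period) will be explored through the intervention × period × patient-group interaction, fitted with all lower-order terms to counts by practice, period and group.*

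The cost is one sentence in the protocol, repeated in the SAP. The data are already to be collected and the sample size does not change. The interval for the three-way term will be wider than for group × year, because it contrasts eight cells where the pooled contrast uses four. With no subgroup power claimed, the result should be reported as an estimate with its interval, and an inconclusive interval should not be read as no difference.
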